6.	Assessment of efficacy	15
7.	Assessment of safety	16
7.1.	Specification, timing and recording of safety parameters	16
7.2.	Procedures for recording and reporting adverse events (AE).....	16
7.3.	Treatment stopping rules.....	16
8.	Statistics	16
8.1.	Sample size	17
8.2.	Analysis.....	17
9.	Quality assurance	18
10.	Direct access to source data and documents.....	18
11.	Ethics and regulatory approvals.....	18
12.	Data Handling.....	19

13. Data Management.....	19
14. Translational research	19
15. Publication Policy	19
16. Insurance/Indemnity	20
17. Financial Aspects	20

1. Study Synopsis

Title of clinical trial	Effect of interceptive strategies on the clinical outcome of impacted maxillary permanent canines.
Protocol Short Title/Acronym	Impacted Canines
Sponsor name	UZ Leuven
Principal Investigator	[name]. [name]
Medical condition or disease under investigation	Maxillary permanent canine impaction
Purpose of the clinical trial	Prospective interventional study of maxillary permanent canines using classic interceptive measures for preventing impaction
Primary objective	To define the most optimal interceptive action for prevention of maxillary permanent canine impaction
Secondary objective (s)	To predict the risk of maxillary permanent canine impaction in young children
Trial Design	International Prospective Interventional Study
Endpoints	Eruption of maxillary permanent canines into the occlusal plane of the dentition.
Sample Size Estimation	For 80% power, 78 subjects needed in each group (for a 50% (nCLA) and 75% success rate (nCLB)). To increase the amount of information for the development of a prediction model for success at 18 months (2nd aim of the study) we need to increase the sample to 100/group (300 patients in total).
Summary of eligibility criteria	Untreated impacted maxillary canines with incomplete root formation, no resorption, no syndromes, no radiotherapy
Maximum duration of interceptive treatment of a subject	6 months
Minimum duration of interceptive treatment follow-up of a subject	6-18 months
Version and date of final protocol	Version 4.0 April 18, 2016
Version and date of protocol amendments	

2. Background and rationale

Maxillary canines contribute significantly to the function and esthetics of the permanent dentition. Completion of their development occurs relatively late. The germs are situated high in the maxilla of three year old children and canine crowns are mesially and palatally inclined. During eruption, the canine migrates down and forward towards the occlusal plane, while the tooth becomes gradually more upright until it reaches the distal aspect of the lateral incisor root and the mesial aspect of the deciduous canine's root apex. Deviation from the standard path of eruption leads to maxillary canine impaction possibly affecting neighboring tooth structures, i.e. causing mild to severe root resorption. Unfortunately, the incidence of maxillary permanent canine impaction is 1 to 3% and its treatment often requires surgical intervention. The purpose of surgically exposing the canine is to enable correction of the pathological path of eruption by applying orthodontic traction guiding the canine to its natural position in the dental arch. Simple interceptive measures taken at early age such as maxillary arch expansion or deciduous canine extraction have been advocated as successfully interfering with the pathological eruption of maxillary canines, avoiding the need for surgery and reducing the orthodontic treatment time and complexity.

3. Trial objectives and Design

3.1. Trial objectives and definitions

The purpose of this study is to detect the differences, if any, between three well known, validated interceptive measures in case of maxillary permanent canine impaction, and to prospectively follow up on these treated patients until further permanent canine alignment in the dental arch is achieved. This long term follow up is necessary in order to evaluate the effects of the interceptive treatment on permanent maxillary canine eruption.

In the present study, a **maxillary permanent canine impaction** would be defined as the inability of this tooth to erupt, failure of eruption, deviation of the canine from its normal eruption pathway or retention of the canine in the maxilla.

Success of a particular interceptive measure would be defined as eruption of the canine without the need for surgical intervention and integrity of the adjacent teeth.

3.2. Primary endpoints

The primary objective is to search for the most optimal interceptive action to prevent maxillary permanent canine impaction.

3.3. Secondary endpoints

The secondary objective is to evaluate whether based on the observations of the present study prediction of maxillary permanent canine impaction in young children is feasible.

3.4. Trial Design

The present trial is a non-commercial prospective randomized controlled trial of patients presenting with permanent maxillary canine impaction. These patients are selected at the intake consultation of the department of Orthodontics, UZ Leuven. A panoramic radiograph is the standard radiographic examination procedure at this particular moment in time for visualization of dental development and associated pathology. Maxillary permanent canine impaction may be diagnosed based on this radiograph by analysing predefined parameters correlated with maxillary permanent canine impaction. In case of signs of mild to severe canine impaction, an additional standard long cone apical radiograph (LCAR) is taken radial to the dental arch at the estimated normal permanent canine position to detect possible root resorption of the adjacent lateral incisor and to document the vertical permanent canine position. A CBCT will only be taken in the following two cases: evidence of damage to the adjacent teeth and for the purposes of canine exposure surgery. Specific inclusion and exclusion criteria are described in paragraph 4.

Patients are stratified based on the presence of a cross bite (Group C) versus no cross bite (Group nC), either a frontal or a uni-/bilateral cross bite. Further categorization is performed for both groups C and nC into 3 subgroups, A, B and C, depending on the obtained parameters related to canine position and angulation. Subgroup CA contains the rather normally positioned canines, indicative for rather normal maxillary permanent canine eruption. This group will function as the control group within Group C. Badly positioned canines will be categorized into subgroup CB constituting the study group. Finally subgroup CC includes those canines that are extremely badly positioned (see paragraph 4) requiring specific additional action.

Cross bite group.

In line with normal standard treatment procedures, the **cross bite group** (Subgroups CA, CB and CC) will receive interceptive maxillary expansion (IME) using the standard techniques that are available and commonly applied in the university hospital. Patients in Subgroup CC, after receiving interceptive expansion treatment, will be further subjected to extraction of the deciduous canine (EX-III), whenever still present in the dental arch, and, depending on the severity of canine angulation and position, of the first deciduous molar (EX-IV). Decision for extraction of one or both of these deciduous teeth will be the responsibility of the treating dentist who will have to evaluate the clinical circumstances presenting in this patient with very badly positioned permanent maxillary canines (Subgroup CC).

After this IME intervention, including III-EX or not, all patients will be enrolled in a standard follow up protocol, requiring a maximum of 3 recall visits at 6, 12 and 18 months.

Non cross bite group.

The **non-cross bite group (Group nC)** will be further allocated in two groups based on the available space in the dental arch, commonly determined in the discipline of orthodontics with the Arch Length

Discrepancy (ALD) methodology: lack of space (subgroup L) versus normal adequate space (subgroup N) for tooth alignment in the dental arch. The lack of space subgroup L may show symptoms of inadequate space in the dental arch such as 'no spacing in the deciduous dentition', 'rotated maxillary permanent incisors', 'space lack for eruption of maxillary permanent lateral incisors', etc.

Both categories in this **non cross bite group (Group nC)**, -either lacking space or displaying normal adequate space for tooth alignment- will consist of four subgroups, including A, B and C, as detailed above, plus subgroup D, in the case of absence of deciduous maxillary canines (due to premature loss or extraction).

1. Non cross bite group with lack of space.

Patients without cross bite but lacking space in the dental arch are subcategorized into the following 4 subgroups:

Patients in **Subgroup nCLA**, constituting patients with no cross bite present but lacking space for adequate tooth alignment in the dental arch, will be randomly attributed to one of our three usual treatment options, being interceptive maxillary expansion (IME), extraction of the deciduous canines (EXIII), or no treatment (CO). The latter will constitute the control group within Group nCLA, indicative for maxillary permanent canine eruption in case of lack of space in the dental arch. After this interceptive treatment, all the patients will be enrolled in a standard follow up protocol. In case of absence of deciduous maxillary canines, randomization will not be possible. These patients will still be treated with expansion because of the lack of space and will also be enrolled in subsequent follow-up.

Patients in **Subgroup nCLB** will also be randomly attributed to one of these three usual treatment protocols, being interceptive maxillary expansion (IME), extraction of the deciduous canines (EXIII), or no treatment (CO). The latter will constitute the control group within Subgroup nCLB. After this interceptive treatment, all the patients will be enrolled in a standard follow up protocol. In case of absence of deciduous maxillary canines, randomization will not be possible. These patients will still be treated with expansion because of the lack of space and will also be enrolled in subsequent follow-up.

Subgroup nCLC, constituting the patients with no cross bite present but lacking space for adequate tooth alignment in the dental arch and with very badly positioned and angulated permanent maxillary canine(s), will receive interceptive maxillary expansion (IME) using the standard expansion techniques described above and commonly applied in the university hospital. Patients in Subgroup nCLC, after receiving interceptive expansion treatment, will be further subjected to extraction of the deciduous canine at 6month follow-up, whenever still present in the dental arch, as well as, depending on the severity of canine angulation and position, of the first deciduous molar. Decision for extraction of one or both of these deciduous teeth will be the responsibility of the treating dentist who will have to evaluate the clinical circumstances presenting in this patient with

very badly positioned permanent maxillary canines. Sequence of eruption other than 3-4-5 will also constitute a criterion for extraction of these deciduous teeth.

After this interceptive treatment, which will last for a maximum of 6 months, all patients will be enrolled in a standard follow up protocol, requiring a minimum of 3 recall visits at 6, 12 and 18 months.

[figure not shown]
2. Non cross bite group with normal adequate space.

Accordingly, Group nCN will constitute all other eligible patients, consecutively seen at the first consultation of the Department of Orthodontics, with one/two impacted permanent maxillary canines without cross bite and showing normal adequate space in the dental arch for tooth alignment. Also these subjects will be categorized into the three subgroups A, B and C. They will receive no interceptive treatment (CO) at all except for subgroup nCNC, constituting of patients with normal alignment and adequate amount of space present but presenting with very badly positioned and angulated permanent maxillary canines. They will be further subjected to extraction of the deciduous canine (EX-III), whenever still present in the dental arch, as well as, depending on the severity of canine angulation and position, of the first deciduous molar (EX-IV). Decision for extraction of one or both of these deciduous teeth will be the responsibility of the treating dentist who will have to evaluate the clinical circumstances presenting in this patient with very badly positioned permanent maxillary canines. Sequence of eruption in the maxilla other than 3-4-5 (canine, first and second premolar) will also constitute a criterion for extraction of these deciduous teeth

After this intervention, all patients in this Subgroup nCN will be enrolled in a standard follow up protocol, requiring minimum one recall visit at 12 months for follow up of normal eruption, eventually a second one after 24 months, provided the maxillary permanent canine is not erupted yet, its root is still not completely formed and no other orthodontic treatment needs are present.

All subjects included in this trial will eventually be subjected to the described follow up procedures, which are described in more detail in Chapter 5. The follow up procedure is designed in order to detect positional changes of the permanent canine position, either spontaneous changes in the control group or changes associated with the interceptive measures taken. Follow up is a necessary and standard procedure for pointing out impacted canines and their true indication for surgical exposure of this tooth.

3.5. Study diagram

3.6. Trial Flowchart

	Screen visit	Record collection	Third visit	Follow up 6 months	Follow up 12 months	Follow up 18 months	Follow up End result
Informed consent		X					
Physical/Oral examination	X			X	X	X	X
Clinical photograph (if needed)		X		X	X	X	X
Panoramic radiograph (if needed)	X						X
Long cone apical radiograph (if needed)	X			X	X	X	
CBCT scan (if needed)					X		
Identification as potential inclusion in the study	X						
Inclusion in one of the groups and randomized treatment assignment		X					
Start of the assigned treatment (expansion, extraction deciduous canine/molar or no treatment)			X	X	X	X	
Surgical exposure of the maxillary permanent canine					X	X	

4. Selection and withdrawal of subjects

4.1. Inclusion criteria

- General inclusion criteria:
 - Female or male patients coming to the department of Orthodontics of the UZ Leuven seeking for orthodontic advice.
 - Presenting with one or two non-fully erupted or impacted maxillary permanent canines (If bilateral impaction occurs, categorization into the different protocol groups will be based on the canine showing the worst position.)
 - Presenting with one or two maxillary permanent canines showing no more than $\frac{3}{4}$ root formation.
 - Any race
- In case of cyst around the area of the impacted canine, extraction of the persisting deciduous canine will be the treatment of choice. Also these cases will remain in follow up according to

our protocol but will not be randomized or attributed in one or other group. Specific canine related inclusion criteria for the allocation of patients in 3 different groups based on the presence of a cross bite (Group C), the absence of a cross bite with lack of space in the dental arch (Group nCL) and the absence of a cross bite with normal adequate space dimensions present in the dental arch (Group nCN):

- Group C (cross bite present)
 - Presence of a cross bite for all three subgroups: uni/bilateral/anterior cross bite. If end-to-end cross bite is present or tendency to cross bite, this will be considered as cross bite
 - Group CA: canine position sector ≤ 1 .
 - Group CB: canine position sector > 1 .
 - Group CC: canine position sector > 1 , canine angulation towards the midline $\geq 45^\circ$.
- Group nCL (no cross bite present)
 - Absence of cross bite and lack of space in the dental arch.
 - Group nCLA: canine position sector ≤ 1 .
 - Group nCLB: canine position sector > 1 .
 - Group nCLC: canine position sector > 1 , canine angulation towards the midline $\geq 45^\circ$.
- Group nCN (no cross bite present and normal space conditions in the dental arch)
 - Absence of cross bite and normal space conditions in the dental arch.
 - Group nCNA: canine position sector ≤ 1 .
 - Group nCNB: canine position sector > 1 .
 - Group nCNC: canine position sector > 1 , canine angulation towards the midline $\geq 45^\circ$.

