4.2. Exclusion criteria

- Fully erupted permanent canines
- Previous orthodontic treatment.
- Canines with completed root formation

- Evidence of root resorption of adjacent teeth or root malformation of the canines that would obligate to extract any adjacent teeth or the canine(s).
- Craniofacial syndromes
- Systemic disease that would impede orthodontic treatment/surgery
- Recent exposure to radiotherapy.

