8.1. Sample size

Randomisation into expansion, extraction and control will be applied for patients without cross-bite having lack of space and – based on canine position and angulation - belonging to strata nCLB and nCLA. Within each of both strata, a randomisation will be performed using permuted blocks of varying size, yielding an equal number of patients in each of the three groups.

Success of the approach is defined as eruption without necessity of surgical intervention and integrity of the roots of the adjacent teeth. The primary endpoint is defined as the percentage success after 18 months. The trial is powered to show a difference between any of the pairs of groups. To have at least 80% power to show a higher success rate in one group compared to the other group, there are 78 subjects needed in each group assuming a success rate of 50% in the first group and 75% in the second group. The calculation is based on a two-sided χ^2 -test with alpha set at $0.05/3=0.0167$ to control the family-wise error rate at 5% (3 pairwise comparisons). However, to increase the amount of information for the development of a prediction model for success at 18 months (cfr. second aim of the study) it has been decided to increase the number of patients to 100 per group (300 patients in total).

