8.2. Analysis

The analysis of the primary endpoint will be based on a stratified χ^2 -test using a Bonferroni-Holm correction to correct for multiple testing (the strata are nCLB and nCLA). The same approach will be used for the comparison at the earlier timepoints (6 and 12 months). No interim analyses are planned, neither for efficacy, nor for futility. The analysis will be performed on an intent-to-treat basis.

A multivariable logistic regression model will be used to predict maxillary permanent canine impaction (=lack of success) on all included subjects. A backward selection procedure will be applied with 0.157 as critical level for the p-value. This critical value corresponds to the use of the Aikake Information Criterion (AIC) for model selection. With AIC we require that the increase in model χ^2 has to be larger than two times the degrees of freedom. This strategy provides a trade-off between erroneous inclusion and exclusion of covariates in a prediction model (Sauerbrei W. The use of resampling methods to simplify regression models in medical statistics. *Applied Statistics* 1999;48 (3):313–329.). The considered predictors are: strata formed by presence of cross-bite and parameters related to canine position and angulation, non-eruption, interceptive strategy, patient's age, stage of canine root formation, premature loss of deciduous teeth, familial history, space deficiency (arch length discrepancy).

As a sensitivity analysis, the prediction model will also be applied separately on the patients from the randomized and non-randomized part of the study.

9. Quality assurance

During this randomized clinical trial only standard operating procedures will be employed, such as i.e. removable expansion device, fixed expansion device, headgear, etc.. They are all validated, thoroughly described and widely used techniques. It will be up to the treating professional to decide for a given case which procedure to follow, in line with existing traditions in the specific collaborating centres. However, the main purpose should be attained which is expansion or in other words gaining extra space for tooth alignment. Depending on the interceptive treatment to be accomplished, decision will be taken to employ one specific treatment protocol to reach the goal set forward.

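### The primary test in 8.2 is valid but ignores age and root-formation stage at entry, giving up precision that is nearly free to recover

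*Combined protocol and SAP*

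**What the plan says.** Eligibility limits maturity only from above. Section 4.1 admits patients with "one or two maxillary permanent canines showing no more than" three-quarter root formation, and section 4.2 excludes "Canines with completed root formation". Neither gives a minimum root stage or an age range.

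The two randomised strata, nCLA and nCLB, are separated in 4.1 by canine sector. Section 8.1 states: "Within each of both strata, a randomisation will be performed using permuted blocks of varying size". The primary endpoint there is the percentage of successes at 18 months. Section 8.2 analyses it with a stratified chi-square test, "using a Bonferroni-Holm correction to correct for multiple testing (the strata are nCLB and nCLA").

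Age and root stage appear in 8.2 only in the secondary logistic model for lack of success, whose candidate predictors include "interceptive strategy, patient's age, stage of canine root formation, premature loss of deciduous teeth". That model uses all included subjects and backward selection at p = 0.157. It is repeated separately in the randomised and non-randomised patients as a sensitivity analysis.

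**The concern.** Success requires eruption by a fixed date, so a canine's maturity at entry could plausibly affect whether it succeeds by 18 months. The plan treats this as possible, because it names age and root stage as candidate predictors. Both can be known before randomisation: root stage must be judged to apply 4.1 at all.

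The comparison that decides the trial uses neither. If the two variables are prognostic, an unadjusted comparison leaves explainable variation in the error term, and each of the three pairwise tests is less sensitive than the same patients would allow. Adjustment is most credible when fixed in advance, so the place to settle it is the current text of 8.2.

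**Working it through.** **1. The plan's own figure.** Inputs from 8.1: 50% vs 75% success, two-sided alpha 0.05/3 = 0.0167, power 80%, equal allocation. With pooled variance and no continuity correction:

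n = [z(1−α/2)·√(2·p̄·q̄) + z(0.80)·√(p1q1 + p2q2)]² / (p2 − p1)²

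- p̄ = 0.625, so √(2 × 0.625 × 0.375) = 0.6847
- √(0.25 + 0.1875) = 0.6614
- n = [2.394 × 0.6847 + 0.8416 × 0.6614]² / 0.25² = (1.6390 + 0.5567)² / 0.0625 = 77.1, rounded up to **78**, as stated

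Power at n per group is Φ{(0.25·√n − 1.6390) / 0.6614}:

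- n = 78: Φ(0.860) = 80.5%
- n = 100: Φ(1.302) = 90.3%

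The 50% and 75% are overall rates, averaged over whatever mix of maturity enrols. These powers therefore do not depend on how strongly maturity predicts success.

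**2. Validity without adjustment.** Two arms of 100 were simulated with a standard-normal maturity covariate, a logistic outcome, alpha 0.0167, two equal strata and an assumed stratum log-odds of 1.0. With no treatment effect, the planned stratified test and the adjusted test each rejected in about 1.4–2.2% of runs, against a nominal 1.67%.

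**3. Gain from adjustment.** In the same set-up, intercepts were chosen to hold the overall success rates fixed. The gain is the power of the adjusted logistic test minus that of the planned stratified test. The maturity effects are assumptions.

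| Maturity log-odds per SD (odds ratio) | Gain at 50% vs 75% | Gain at 50% vs 70% |
|---|---|---|
| 0 (1.0) | none | none |
| 0.4 (1.5) | about 1 point | about 2–3 points |
| 0.7 (2.0) | about 2 points | about 6 points |
| 1.1 (3.0) | about 5 points | about 11 points |
| 1.6 (5.0) | about 6 points | about 17 points |

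Only the 50% vs 75% column uses the plan's rates. The 20-point column is an added scenario.

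**4. Cross-check.** A separate simulation (3,000 runs per setting, 50% vs 75%) used an unstratified two-proportion test as comparator. Power, unadjusted then adjusted:

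- odds ratio 1.5: 91.1% and 92.6%
- odds ratio 2: 90.0% and 93.0%
- odds ratio 3: 90.7% and 95.6%
- odds ratio 4: 90.4% and 97.1%

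The gains are 1.5, 3.0, 4.9 and 6.6 points, in line with the table within simulation error.

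**The case against.** The strongest reply is that nothing is broken: allocation is random, type I error holds, and 100 per group exceeds the 80% target with no adjustment. All of that stands, and it limits the point to efficiency.

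It can also be said that 8.2 already has an adjusted analysis, since the prediction model contains strategy, age and root stage and is rerun in the randomised patients. This stands in part. The model is secondary, the rerun is a sensitivity analysis, and backward selection may remove age, root stage or strategy. It therefore guarantees no pre-specified adjusted treatment contrast.

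Three stronger readings are tempting, and the documents do not support them.

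- *Imbalance in maturity would pass for a treatment effect.* Imbalance by chance is not rare. In a maturity class holding an assumed 30–50% of patients, at least one of the three pairs of arms differs by 10 points or more in about 31–37% of trials of this size. But this is random error that alpha already covers, as step 2 shows.
- *The missing lower limit in 4.1 is itself the defect.* Very immature entrants might lower success in every arm. But the documents give no distribution of age or root stage and no share of such patients, and the 50% and 75% are already overall rates. Covariate adjustment would not cure that dilution either.
- *The protocol says that maturity drives the timing of eruption.* It does not. Section 2 says of the canines only that "Completion of their development occurs relatively late", and 8.2 lists age and root stage as candidates open to elimination. The recall rule for group nCN in 3.4, which depends on incomplete root formation, is indirect support at most.

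**Conclusion.** The point holds as a cheap improvement to 8.2. The planned primary test is sound and meets its stated power, but it leaves unused two baseline variables that the plan itself considers possible predictors.

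The benefit is about 1 to 6 power points per pairwise comparison at the plan's 50% vs 75% and 100 per arm. If the true difference were 20 points, it would be about 2 to 17. These figures assume one normally distributed, perfectly measured maturity covariate with log-odds of 0.4 to 1.6 per SD. The upper end is an odds ratio of about 5, which is strong, and the cap on root stage at entry may narrow the spread. If maturity is only weakly prognostic, the gain is near the bottom of the range. If it is not prognostic at all, the simulations show no loss.

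**What to change.** In 8.2, pre-specify each primary pairwise comparison as a test of the arm effect in a logistic regression of 18-month success on:

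- arm
- stratum (nCLA/nCLB)
- baseline root-formation stage of the index canine (in bilateral cases, the worse-positioned canine that 4.1 uses for grouping)
- age

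Record both covariates before randomisation, state how each is coded, and keep them in the model whatever their p-values. Retain the Holm correction over the three comparisons. Report a standardised (covariate-adjusted) risk difference for each pair, and keep the stratified chi-square test as a supportive analysis.

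The cost is SAP wording and two baseline fields already needed for the prediction model. No patients or visits are added, and 4.1 stays as it is. The downside is that the primary test becomes model-based and the odds ratio has to be converted to a risk difference for reporting.
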